As a result of both the successes of the Phase II and Phase III collaborations, and the shortcomings of the Phase I 1308 collaboration, the RETAIN team decided to end our collaboration with 1308 and focus all resources squarely on the Phase II and Phase III collaborations. This decision was discussed with the 1308 investigators on November 27 and the RETAIN team received approval to move forward exclusively focused on Phases II and II from the sponsor, the Nation Cancer Institute, on November 30, 2017.

As a result of this change, the team removed RTOG 1308-relevant language from the IRB protocol and ended Penn's oversight of the RETAIN trial at MDACC, a relying institution. The MGH and Washington University research teams closed out the RETAIN study at their respective sites.

7. Approved January 25, 2018

a. Phase II – Modification to BASC screening procedures

The study teams for BASC and RETAIN implemented a RETAIN-related change to the phone screen script being used at Northwestern and Penn. For patients randomized to RETAIN, the team stopped asking, "Does this sound like something that you are interested in?" before administering the RETAIN surveys. They simply transitioned from introducing the study basics to administering the RETAIN questions by saying, "Now we ask that you answer a few more questions before finalizing the details of your intake visit."

The goal of this change was to provide an opportunity to capture RETAIN baseline data that was not being collected systematically due to early withdraws from the phone screen call.

b. Phases II and III - Revisions to the Compared Riskiness Scale

The study team examined the phrasing for the Compared Riskiness scale in an Amazon mechanical Turk study aimed at countering floor effects in our measure of risk perception. As a result of this investigation we made several changes to the phrasing of the questions in the scale. We did not add new items to the scale.

8. Approved February 21, 2018

a. Phase II – Modification to MOVE IT recruitment procedures

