- 1. Attitudes towards research: Attitudes towards research will be measured using the Research Attitudes Questionnaire-7 (RAQ-7).⁵² The RAQ has high internal consistency and factorial validity.^{53,54} We will measure the RAQ prior to disclosure of incentives in order to 1) assess patients' broad reasons to participate in research or not without being biased by prior discussions of payment 2) assess whether the hypothesized relationship between RAQ score and the odds of enrolling is modified by incentives. The presence of such effect modification would suggest that incentives represent undue inducements.
- 2. Attention to the informed consent document: Attending more carefully to informed consent documents may promote informed choice. ⁵⁵ Visual focus has been established as a measure of attention in several settings, and has been associated with peoples' choices^{56,57} and subsequent recall. ⁵⁸ We will assess the amount of time patients spend reading each part of the parent trial consent form by setting up each section as a "survey" in REDCap. The data extract will include the time to the second at which the participant moved to another section through a timestamp. The primary measure of this assessment will be time spent on the risk section; the secondary measure will be total time spent on the consent form.
- Perceived risks of the research: Perceived risks of the research will be measured by a modified 9-item "compared riskiness" scale, which assesses perceptions of research risk.⁸
- 4. Incidence of therapeutic misconceptions: It has been hypothesized that the use of financial incentives could reduce therapeutic misconceptions, and thereby promote informed decision-making. ⁵⁰ Because patients are not accustomed to being paid for their clinical care, offering incentives could signal that research is different. We will test the hypothesized benefit of research incentives by measuring the incidence of therapeutic

misconceptions in each incentive arm. We will assess this outcome with a 4-item therapeutic misconceptions tool, developed by External Advisory Board member, [name]. ⁵⁹⁻⁶¹

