All participants who are randomized and enrolled in RETAIN and consent to the BASC and MOVE IT will be debriefed on the randomization of incentives and the purpose of the RETAIN study will be explained (see Sections 8.g. and 8.h. Debriefing in BASC and MOVE IT, respectively).

d. Administration of Survey Instruments

i. BASC

Procedures for this study will commence during initial pre-screening eligibility assessment via phone for the BASC trial. During this call, all study candidates will complete an initial eligibility assessment with research staff members from the clinical site from which they are being recruited (Northwestern or Penn). Research staff will begin with the BASC eligibility screen survey, which includes basic demographic questions, as well as questions related to participants' endorsement of symptoms of clinical depression. Once a patient is determined to be preliminarily eligible for BASC, the research staff will ask the RETAIN eligibility prompt to assess for prior knowledge of the specific incentives or randomization used for RETAIN. Participants who do not have prior knowledge of the RETAIN incentives or randomization will be randomized by the research staff via the BASC trial's Data Management System (DMS) (see Section 10.a.1 Data Collection and Data Confidentiality – BASC). Prospective participants will then be introduced to BASC study basics and risks and informed that if they are determined to be eligible for the BASC study and participate in the BASC trial, they will receive \$0, \$200, or \$500 for participation.

Prospective participants who have prior knowledge of the incentives or randomization used for RETAIN will not be randomized, enrolled, or receive RETAIN-related messaging on the phone call. They will receive the standard study information regarding session and travel compensation for the BASC trial without RETAIN messaging. For information on remuneration in the BASC trial, see Section 6.d. These participants will not be debriefed or paid the RETAIN incentives.

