Before research staff finalize logistical details on the BASC study and schedule intakes for tentatively eligible patients, they will administer several RETAIN-related questionnaires to assess 1) demographics and personal financial well-being, 2) attitudes towards biomedical research, 3) prior experience in research, and 4) perceptions of research risk. The screener will administer these surveys via phone using CRF forms adopted for the RETAIN trial that will later be scanned into the BASC trial's DMS.

Participants who pass the BASC pre-screening will be scheduled to attend a 2-3½ hour Intake session for the BASC trial. During the intake session, BASC research staff at Penn and Northwestern will read a pre-BASC consent script before presenting an electronic image of the BASC informed consent/ HIPAA forms with additional information regarding the RETAIN incentive randomization condition; this electronic image will be presented via tablet or desktop. By presenting the BASC consent with randomized compensation information electronically, we will assess the amount of time participants spend reading each part of the main trial consent form. Each section (e.g., Study Introduction, Procedures by Visit, Possible Risks and Discomforts, etc.) will be presented as a survey in REDCap. Time-stamp data collected for this REDCap module will be linked by the study ID generated in the BASC Data Management System during candidates' telephone pre-screen call (see Section 10.a.1. Data Collection and Data Confidentiality - BASC).

Once participants finish reading and before signing a paper version of the BASC trial consent, they will complete brief assessments of perceptions of research risk (administered over the telephone pre-screen and again at intake – see Section 9.a. BASC Study Calendar). They will also complete assessments on perceptions of the difference between research and individualized patient care and understanding of the smoking cessation study via a trial elements quiz. All of these measures will be administered via the CRF paper and pencil processes currently used in the BASC trial. The responses to the quiz will be reviewed with participants, during which participants' questions will be answered.

ii. MOVE IT

Clinical research coordinators will identify patients through electronic health record-based screening for the MOVE IT study and preliminarily eligible patients will be approached for recruitment in their hospital rooms.

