The primary outcome is the proportion of participants assigned to each incentive amount that consent to enroll in each of the two parent RCTs.

b. Primary analytic sample

Intention-to-treat (ITT) approach such that the analytic sample will include all patients randomized in the RETAIN trial, even if ultimately deemed ineligible for the parent trials.

c. Primary analysis

We will first assess bivariate relationships of incentives with the primary outcome using chi-square tests for comparisons of proportions. To examine the hypothesized statistical interactions, we will use logistic, linear, or quantile regression, as appropriate based on outcome parameterizations and distributions. In the above analyses we treated incentive as an ordered variable. In all analyses in which the parent trial enrolls in multiple centers, we will model the center from which patients are recruited as a fixed effect, thereby mitigating confounding by center and adjusting variance estimates for clustering of participants within centers. To adjust for chance covariate imbalance among arms, primary analyses will include covariates (see Table 1) in multivariable models if they are significantly associated with the intervention arm and predictive of enrollment in the parent trials in bivariate analyses. To avoid problems in estimating odds ratios due to sparse data, we will limit the number of covariates to no more than 1 per 10 participants enrolling in the parent trials. In all analyses related to the BASC parent trial, we will model the center from which patients are recruited as a fixed effect, thereby mitigating confounding by centers are recruited as a fixed effect, thereby mitigating confounding by center and adjust related to the BASC parent trial, we will model the center from which patients are recruited as a fixed effect, thereby mitigating confounding by center and adjusting variance estimates for clustering of participants within centers.

Our analyses to rule out undue and unjust inducements entail three primary covariates: risk perception, annual household income, and economic well-being. All models will use enrollment in the parent trial as the outcome. To determine if incentives represent undue inducements for research participation, we will test the statistical interaction between incentive size and the primary covariate of risk perception on

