the outcome of enrollment in the parent trials. We will test two interactions, each in a separate model to avoid collinearity, to determine if incentives represent unjust inducements: that between incentive size and the primary covariate of annual household income, and that between incentive size and the primary covariate of economic well-being. All analyses will be stratified by parent study.

Analyses of interaction terms will be structured as tests of non-inferiority. The null hypothesis, for both trials, will be that the use of incentives meets criteria for undue or unjust inducement. We can reject the null, and conclude the absence of undue or unjust inducement, if the interaction terms are "small" according to pre-specified criteria (in technical terms, the inferiority margin). Said a different way, our analyses are designed to determine if we can exclude the possibility that incentives represent undue or unjust inducements if the resulting interaction terms are sufficiently small. Specifically, we will use one-sided alpha levels of 0.05 to exclude, with 95% confidence, the possibility that any of these interaction odds ratios are >2.0.

We will explore temporal trends in incentives' effects over the study period using stratified analyses. If temporal trends are noted, as may occur if prospective patients learn of the incentives used in these studies, we will adjust for their influence by entering time as a covariate, modeled as a spline. We will evaluate potential effect modifiers (variables in Table 1) using stratified analyses. If differences among strata appear, we will formally test their corresponding interactions with the incentive amount.

TABLE 1 FACTORS FOR ADJUSTMENT AND EXPLORATION OF EFFECT MODIFICATION

Potential factors for adjustment			
Patient level covariates	Variable coding or definition		
• Age	Continuous		
• Gender	Binary		
• Race	Categorical		
Marital status	Categorical		
Education	Categorical		
Income	Categorical		
Economic well-being	Categorical		
Prior research participation	Categorical		
Attitudes towards research:	Continuous, measured using the Research Attitudes Questionnaire-7 (RAQ- 7).		

6. Secondary analysis

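### The final SAP can adjust the enrolment odds ratio for research attitudes measured after the incentive is announced, and leaves MOVE IT's randomisation stratum out of every stated analysis

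*Combined protocol and SAP*

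**What the plan says.** **Adjustment rule.** Final SAP 5.c, under the aim of correcting chance imbalance between arms, says that "primary analyses will include covariates (see Table 1) in multivariable models if they are significantly associated with the intervention arm and predictive of enrollment" in bivariate analyses. It gives no significance level for that selection. Table 1 includes attitudes towards research: "Continuous, measured using the Research Attitudes Questionnaire-7".

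**Stated timing of the RAQ.** Final protocol 3.c, item 1: "We will measure the RAQ prior to disclosure of incentives". One purpose given is to see whether incentives modify the relation between RAQ score and enrolment, and the text adds: "The presence of such effect modification would suggest that incentives represent undue inducements".

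**Procedures.** In BASC (final protocol 8.d.i) the candidate is randomised on the pre-screening call and then hears the assigned sum ($0, $200 or $500), being "informed that if they are determined to be eligible for the BASC study and participate in the BASC trial, they will receive" that amount. Only after that, before the intake is scheduled, "they will administer several RETAIN-related questionnaires to assess 1) demographics and personal financial well-being, 2) attitudes towards biomedical research". In MOVE IT (7.b.ii and 8.d.ii) the patient is randomised, hears the amount in the rest of the recruitment script, and is then registered in the survey platform, where the RAQ is given to those who are still interested.

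**Stratification.** Randomisation is stratified by site in BASC and by clinical research coordinator in MOVE IT (final protocol 7.b; final SAP 3.a and 3.b). Final SAP 5.c models centre as a fixed effect for BASC and for any multi-centre parent trial. MOVE IT has one site (final protocol 4.c). Coordinator is not in Table 1 or in any stated model.

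**The concern.** A covariate measured before the offer can differ between randomised arms only by chance, and adjusting for it is sound. The RAQ is collected after the offer, so an arm difference may be caused by the incentive. The rule is most likely to admit the RAQ when the offer has moved it, and adjustment then removes the part of the incentive effect that runs through attitudes. The resulting odds ratio would be described as corrected for chance imbalance while being net of part of the effect under study, and it would reach significance less often.

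The same timing undercuts item 1 of 3.c. Reading RAQ effect modification as undue inducement relies on a score taken before disclosure.

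In MOVE IT, a test that ignores the stratification factor overstates its variance when consent rates differ between coordinators. That makes the test conservative and costs power. It does not bias the effect: the accompanying change in odds ratio is the usual gap between marginal and conditional odds ratios.

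**Working it through.** **1. Order of events (final protocol)**

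| | BASC (8.d.i) | MOVE IT (7.b.ii, 8.d.ii) |
|---|---|---|
| Randomised | Pre-screening call, after the eligibility screen and prior-knowledge probe | At the bedside, after two screening questions |
| Amount stated | Same call, directly afterwards | Rest of the recruitment script |
| RAQ | Later in the same call | Afterwards, in the survey platform, for interested patients |

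The change log agrees on the order. Item 7.a, on BASC, says: "They simply transitioned from introducing the study basics to administering the RETAIN questions". Item 8.a, on MOVE IT, records the wish to announce the incentive earlier. The sentence in 3.c fits the dropped RTOG 1308 flow, where attitudes were measured before randomisation (original protocol 7.b.i), so it appears to have been carried over.

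**2. Size of the RAQ effect**

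The plan gives no figure to reproduce. From the SAP: 576 patients, 192 per arm. Assumed: direct high-versus-low odds ratio 1.5; RAQ odds ratio 2 per SD; RAQ shift linear over arms; selection at p<0.05.

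*Admission, trend version.* With arms coded 0, 1, 2, the slope's standard error is 1/√(2×192) = 0.0510 SD. A 0.2 SD high-versus-low shift is 0.1 per step, so z = 0.1/0.0510 = 1.96 and admission is about 50%. For 0.1 and 0.3 SD, z = 0.98 and 2.94, giving about 17% and 84%.

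*Odds ratio at 0.2 SD.* Direct part ln 1.5 = 0.405; part through the RAQ 0.2 × ln 2 = 0.139; total 0.544. The unadjusted odds ratio is marginal. With no shift it is 1.43, so it shrinks by ln 1.43/ln 1.5 = 0.88. Then exp(0.544 × 0.88) is about 1.62. Adjusting for the RAQ leaves exp(0.405) = 1.50.

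*Simulation, 4,000 runs per row (admission range is ANOVA to trend; the last three columns take the trend version where the rule applies):*

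| Shift, high vs low | RAQ admitted | OR unadjusted | OR adjusted | OR under rule | Significant, unadjusted | Significant, under rule |
|---|---|---|---|---|---|---|
| 0 | about 5% | 1.43 | 1.49 | 1.44 | 41.1% | 41.2% |
| 0.1 SD | 13–17% | 1.53 | 1.50 | 1.50 | 54.0% | 49.3% |
| 0.2 SD | 40–49% | 1.63 | 1.50 | 1.52 | 65.0% | 51.2% |
| 0.3 SD | 76–83% | 1.75 | 1.51 | 1.52 | 76.7% | 48.8% |

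The gap between 1.43 and 1.49 at no shift is marginal versus conditional, not bias. With an RAQ odds ratio of 1.5 per SD, significance at shifts 0, 0.1, 0.2 and 0.3 SD is 45.7, 53.7, 63.3 and 68.9% unadjusted, against 45.9, 51.0, 54.5 and 50.2% under the rule. If the whole incentive effect ran through the RAQ (odds ratio 2, shift 0.3 SD), the odds ratio would be 1.21 unadjusted and 1.00 adjusted.

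**3. Early MOVE IT decliners (secondary note)**

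As 8.d.ii is written, early decliners have no RAQ, so a model that admits it drops them. Assumed: consent 45/50/55%, no RAQ shift, early decline of 30/25/20% by arm or 30% in every arm. The RAQ is admitted in 5–9% of trials. The odds ratio averaged over the rule is 1.48–1.49 or 1.52–1.53 respectively, against 1.49–1.50 in all randomised patients.

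**4. Coordinator**

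Assumed: six coordinators with 96 patients each, balanced by arm; mean consent 50%; within-coordinator odds ratio 1.6 for power. True variance divided by the variance the unstratified test assumes is 1 − SD²/0.25, which is 0.99, 0.96 and 0.91 for consent-rate SD 0.05, 0.10 and 0.15. The size is 2{1 − Φ(1.96/√ratio)} = 4.9, 4.5 and 4.0%. Simulation (60,000 runs; interaction test 8,000 runs with median split, margin 2.0, one-sided 0.05, true interaction odds ratio 1):

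| SD (range of rates) | Size, unstratified | Size, stratified | Power, unstratified | Power, stratified | Interaction power without / with coordinator |
|---|---|---|---|---|---|
| 0 | 4.6% | 4.6% | 62.1% | 62.1% | 52.7 / 52.7% |
| 0.05 (43–57%) | 4.6% | 4.7% | 61.4% | 61.9% | not run |
| 0.10 (35–65%) | 4.2% | 5.3% | 58.7% | 62.1% | 51.7 / 50.5% |
| 0.15 (28–72%) | 3.7% | 5.0% | 54.1% | 58.6% | 52.8 / 48.5% |

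**The case against.** **Reach.** Final SAP 5.c tests enrolment first with an unadjusted chi-square, which is untouched. Logistic regression is introduced for the interaction tests, and no bias is claimed for those when the true interaction is null. No section names an adjusted incentive odds ratio as the headline result. This stands as a limit. The rule is nevertheless written for the primary analyses, enrolment is the primary outcome, and an adjusted odds ratio is therefore within the plan.

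**Conditional harm.** The offer must move the RAQ, the RAQ must pass two screens, and the adjusted figure must be reported. The RAQ covers broad attitudes, so hearing one study's payment may move it little. This also stands: at 0.1 SD the change in odds ratio is negligible, and a weaker RAQ association shrinks the loss.

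**Undue inducement.** The final SAP uses only risk perception, income and economic well-being for its inducement tests, and the RAQ is just an exploratory modifier. That is correct, so this part is a correction to protocol 3.c.

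**Coordinator.** The number of coordinators and their spread are assumed, and final SAP 3.b describes a scripted process. At SD 0.15 stratifying gains 4.5 points on the enrolment test and loses 4.3 on the interaction test, the kind of test that sized the trial. Part of the gain at SD 0.10 reflects a stratified size of 5.3%. On its own this would be a minor point. It remains that BASC's stratum is modelled and MOVE IT's is not.

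**Pre-named list.** With no shift, the selection rule does no visible harm, so removing the RAQ alone answers the demonstrated problem. Naming covariates in advance is the cleaner form, but it goes further than the figures require.

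**Conclusion.** The concern holds, and the plan should be changed. The contradiction between item 1 of 3.c and the procedures is in the text and needs no assumption. So is the absence of MOVE IT's stratification factor from the stated analyses.

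The numerical harm is conditional. It is nil without an RAQ shift and negligible in the odds ratio at 0.1 SD. At 0.2–0.3 SD with an RAQ odds ratio of 2 per SD, the rule costs about 14 to 28 percentage points in the chance of a significant enrolment odds ratio (65.0 − 51.2 and 76.7 − 48.8). At an RAQ odds ratio of 1.5 the cost is about 9 to 19 points (63.3 − 54.5 and 68.9 − 50.2). The coordinator omission leaves a size of 3.7–4.6% and costs up to 4.5 points of power over the spreads assumed. The RAQ shift, the RAQ odds ratio, the early-decline rates and the number and spread of coordinators are all assumptions.

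**What to change.** 1. Take the RAQ out of the Table 1 adjusters and report it by arm descriptively.
2. Replace selection by significance with a short pre-named list of covariates that the offer cannot alter and that are held for all randomised patients. Basic demographics are candidates. In BASC, "Research staff will begin with the BASC eligibility screen survey, which includes basic demographic questions", which comes before randomisation. For MOVE IT, change-log item 9.a says demographics could be captured for decliners, but 8.d.ii places that questionnaire after the amount and only for interested patients, so availability must be confirmed.
3. Reconcile item 1 of 3.c with 7.b and 8.d: state that the RAQ is collected after disclosure, and drop the reading of its effect modification as undue inducement.
4. Add coordinator as a fixed effect in the MOVE IT logistic models and as strata in its trend test, as is done for site in BASC.

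The cost is SAP wording, one protocol correction, and a factor already used for the randomisation lists. Coordinator takes a few degrees of freedom (five for six coordinators) and somewhat lowers the power of the MOVE IT interaction test if coordinators differ, as tabulated above. Removing the RAQ does not repair the wider loss of questionnaire data among early MOVE IT decliners.

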Participants will be randomized to the 3 experimental arms (low-, middle-, and high-level incentive) in equal, 33.3% probabilities. A Penn analyst will implement block randomization stratified by site in the BASC parent trial and stratified by clinical research coordinator in the MOVE IT trial. The trial's primary statistician on the Penn research staff will provide a block randomization scheme for each clinical research coordinator (MOVE IT) and will upload a CSV file to the REDCap randomization module. He/she will also provide a block randomization scheme for each site for the Access Data Management System (BASC) (see Section 10.a.1. Data Management – BASC). The parent trial research staff will respond to initial eligibility prompts n the REDCap software through an initialization step and will immediately receive the randomization assignment for that participant. Randomization will take place in the DMS for the BASC trial. This will allow them to message to the participant the appropriate incentive level for participation in the parent trial, and present the correct paper consent based on their arm assignment (see Sections 8.g. Parent Trial Informed Consent).

i. BASC

Randomization and group assignment occurs after pre-screening data are collected and RETAIN eligibility probes are administered on the eligibility pre-screening call for the BASC parent trial (see Section 8.e.2 Administration of Survey Instruments – BASC). Research staff will know group assignment when patients are first introduced to the BASC trial on the phone in order to message the assigned payment (\$0, \$200, \$500) for the participant. Participants who are deemed preliminarily eligible will schedule an intake session, where they will view the electronic BASC parent trial consent form (\$0, \$200, or \$500) and receive a paper copy of the form with respective incentive information.

ii. MOVE IT

Randomization and group assignment occur after MOVE IT screening steps (see Section 8.e.3 Administration of Survey Instruments – MOVE IT) following clinical research coordinators' brief introduction to the study upon entering patients' hospital room. Clinical research coordinators will randomize patients and know the group assignment as they complete the recruitment script and assess patients' interest in learning about the MOVE IT trial. Assignment occurs prior to registering the patient in the Way to Health platform used for survey administration.

8. Study Procedures

a. Screening

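### Final SAP 5.c tests Table 1 covariates against the randomised arm before adjusting for them: good predictors are mostly left out, an adjusted enrolment model loses about 2 to 5 points of power, and the odds ratio compared with 2.0 is not fixed in advance

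*Combined protocol and SAP*

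**What the plan says.** Final SAP section 5.c (Primary analysis) gives the purpose of the rule as "To adjust for chance covariate imbalance among arms". It then says that "primary analyses will include covariates (see Table 1) in multivariable models if they are significantly associated with the intervention arm". A second condition is joined to this one: the covariate must also predict parent-trial enrolment when tested on its own. Both conditions must hold. No significance level is given for either. The candidates are the nine variables under "TABLE 1 FACTORS FOR ADJUSTMENT AND EXPLORATION OF EFFECT MODIFICATION", and covariates are capped at one per 10 patients enrolling in the parent trial.

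Some terms enter without any test. For BASC, "we will model the center from which patients are recruited as a fixed effect". Each interaction model contains its own member of the "three primary covariates: risk perception, annual household income, and economic well-being". Time may be added as a spline if trends are seen.

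Section 5.c opens with chi-square tests of incentive against enrolment, and then turns to regression for the interactions. Each interaction odds ratio is compared with a fixed margin of 2.0. Section 7.b sizes each sub-trial on the risk-perception interaction and does not mention covariate adjustment.

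On timing, Final Protocol 7.b.i (BASC) says "Randomization and group assignment occurs after pre-screening data are collected". For MOVE IT, section 8.d.ii says "Clinical research coordinators will identify patients through electronic health record-based screening for the MOVE IT study".

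**The concern.** Patients are randomised 1:1:1, so a variable fixed before the offer can be associated with arm only by chance. The first condition therefore carries no information on whether the variable is worth adjusting for, yet it decides entry. A variable that strongly predicts consent is nearly always dropped, and the rule behaves almost like no adjustment.

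Two things are at stake. In a logistic model of enrolment on incentive, leaving out strong predictors pulls the incentive odds ratio towards 1 and loses power. Odds ratios are also non-collapsible: adjusted and unadjusted interaction odds ratios are different quantities. If chance selects the covariates, the SAP does not say in advance which of the two is compared with 2.0.

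**Working it through.** **1. The plan's own figure.** Section 7.b states at least 80% power with 96 patients per cell, 50% enrolment, a true interaction OR of 1, margin 2.0 and one-sided alpha 0.0427 (z = 1.720). Power = Φ(ln 2/SE − z), with ln 2 = 0.693.
- Full four-cell interaction: SE = √(16/96) = 0.408, so Φ(1.698 − 1.720) = 49.1%.
- OR in the top-incentive arm alone: SE = √(8/96) = 0.289, so Φ(2.401 − 1.720) = 75.2%.

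Neither gives 80%. The SAP expects more from analysing risk as continuous, which cannot be checked from its inputs. That is a separate point; it matters here because it explains the baseline of about 48% in step 4.

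**2. How often the screen drops a covariate.** For a variable that the offer cannot change, the omission rate is at least 1 − alpha, however predictive it is: 99%, 95%, 90% and 80% at alpha 0.01, 0.05, 0.10 and 0.20. The chance that at least one of nine independent covariates passes the arm test at 0.05 is 1 − 0.95⁹ = 37%; fewer will also predict enrolment. The cap does not require a screen: Final Protocol 6.a expects 288 enrollers, and 288/10 allows 28 terms.

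**3. Enrolment model.** Simulation of 4,000 trials per setting: 576 patients, 192 per arm, ordered incentive, two-sided 0.05. Assumed: top-versus-low OR 1.8, and one predictor with OR 1.5, 2 or 3 per SD (log-odds SD 0.41, 0.69, 1.10).

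| Predictor OR per SD | No adjustment | SAP rule at 0.05 | Always adjusted | Gain over SAP rule |
|---|---|---|---|---|
| 1.5 | 78.4% | 78.5% | 80.2% | 1.7 |
| 2 | 72.6% | 72.8% | 77.2% | 4.4 |
| 3 | 63.1% | 63.5% | 74.0% | 10.5 |

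Two sets of runs with three to six covariates, comparing the SAP rule with a fixed list, gave:
- combined log-odds SD 0.4: 73 v 77% and 74.3 v 76.6%
- SD 0.6: 71 v 75% and 71.1 v 75.4%
- SD 0.8: 67 v 72% and 70.0 v 76.7%

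Over this range the gain is roughly 2 to 5 points, with one result of 6.7.

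**4. Non-inferiority interaction.** Same single-predictor simulation, true interaction OR 1, risk split at the median, alpha 0.0427.

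| Predictor OR per SD | SAP rule | Always adjusted | SE unadjusted → adjusted |
|---|---|---|---|
| 1.5 | 47.9% | 47.2% | 0.414 → 0.423 |
| 2 | 48.0% | 45.9% | 0.414 → 0.436 |
| 3 | 48.0% | 42.0% | 0.413 → 0.462 |

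Adjustment lowers power by 0.7, 2.1 and 6.0 points. The true log-OR is 0 either way and the margin is fixed, so only the larger SE counts. Check for the last row: Φ(0.693/0.462 − 1.720) = Φ(−0.22) = 41%.

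**5. Which odds ratio meets the margin.** With a true conditional interaction OR of 2.0 (log-OR 0.693), the mean unadjusted estimates were 0.677, 0.641 and 0.552, that is ORs of 1.97, 1.90 and 1.74. Inducement was then wrongly ruled out in 4.9%, 5.4% and 8.4% of trials under the SAP rule, against 4.2%, 3.8% and 4.5% with fixed adjustment (nominal 4.27%). Simulation error is about √(0.0427 × 0.9573/4000) = 0.3 points, and the rate was 4.7% with no predictor at all, so only the last figure is clearly raised.

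**6. Which variables the offer cannot change.** Final Protocol 8.d has patients in both parent trials told the amount before the surveys on finances, research attitudes and prior research experience. Section 3.c says instead that attitudes are measured before disclosure; the two need reconciling. The RETAIN demographics survey also follows disclosure, and in MOVE IT only patients who want to learn more reach it. The BASC eligibility screen asks basic demographic questions before randomisation. MOVE IT patients are found through the health record, but the documents do not say which items are kept for every randomised patient.

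**The case against.** The strongest reply is that the trial is sized on the interaction tests and its first aim is ethical, and there adjustment reduces power. That stands. A reader might infer from the rule that the trial's main tests are losing power; step 4 shows the opposite.

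Second, the chi-square comparison of enrolment is unadjusted whatever the covariate rule says, and the SAP change table calls it a single test. That also stands, so the power loss concerns only a regression estimate of enrolment. But section 5.c wants centre as a fixed effect in all BASC analyses, which needs a model, and the SAP does not say which estimate is primary.

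Third, a reader might infer that the models adjust for nothing but imbalanced covariates. BASC centre, each interaction model's own primary covariate and possibly time contradict that.

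Fourth, if covariates seldom enter, the estimand seldom changes, and the cells of 96 in section 7.b suggest that 2.0 was meant as an unadjusted odds ratio. This has force: the raised error in step 5 comes almost wholly from not adjusting (8.6% with no adjustment at all, against 8.4% under the rule). What remains is that up to 37% of trials could have some covariate pass the arm test, and the SAP leaves the reading of the margin open.

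Fifth, adjusting for survey items answered after disclosure could drop early decliners from the intention-to-treat sample, or adjust for something the offer has changed. That is right, and it limits the list proposed below.

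**Conclusion.** The point holds in a limited form. The screen leaves out predictors that the offer cannot change about 95% of the time at an assumed 0.05 level. That costs an adjusted enrolment model roughly 2 to 5 points of power and leaves the odds ratio behind the 2.0 margin unsettled. It should be changed, but it does not invalidate the trial.

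The size rests on assumptions that are not in the documents: the level of the arm test, the covariate strengths, the incentive effect and equally spaced incentive scores. Two larger figures should not be read into it:
- Losses of 7 to 12 points (69 v 76% and 62 v 74%) need eight covariates with combined SD 0.9 to 1.2. Without income, economic well-being and attitudes, Table 1 leaves 9 − 3 = 6, and fewer can be confirmed as recorded for everyone before disclosure.
- The 8.4% error rate needs a predictor with OR 3 per SD and a margin read as conditional. The documents state neither.

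The 95% figure does not carry over to survey items answered after disclosure. The offer itself may shift those answers, and they may then pass the arm test more often.

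**What to change.** - Delete the test of association with arm from Final SAP 5.c.
- For each parent trial, name now a fixed list of variables that the offer cannot change and that are recorded for every randomised patient. Age, gender and race are candidates, if confirmed available from screening or the health record.
- Leave out income, economic well-being, research attitudes and anything else asked only after disclosure. Do not make entry depend on completeness, which would again let the data choose the list.
- State that the enrolment model adjusted for this list, with centre in BASC, gives the primary enrolment estimate.
- Use one pre-named set, either the same list or none, in all three interaction models, beside each model's own primary covariate. State whether the 2.0 margin is conditional on it.

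The cost is SAP wording and a check of what screening records hold. If the list is used in the interaction models, expect no gain in non-inferiority power and a likely loss of about 1 to 2 points, up to about 6 with very strong predictors.
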